# APPENDIX B EQUIPMENT LIST

The following equipment may be supplied to an investigative site for the duration of the study provided that the site does not already have such equipment available for use. This equipment loan will be documented in the Cooperative Research and Development Agreement (CRADA) CRADA, which indicates that the equipment is to be returned to Abbott Medical Optics at the completion of the study.

- iDesign Advanced WaveScan Studio System
- One Vector Vision CSV-1000 ETDRS visual acuity light box, stand
- Three Vector Vision ETDRS 4.0 meter distance charts (100% contrast)
- Vector Vision Contrast Sensitivity charts
- Light Meter
- Tape measure (meters)
- Trial lenses

## APPENDIX C MANUAL OF TESTING PROCEDURES

**Anterior Segment Examination** shall be performed via biomicroscopic slit-lamp exam for determination of anterior segment medical findings including but not limited to the adnexa, conjunctiva, sclera, cornea, and iris. The cornea should be examined in detail and corneal clarity should be graded based on the scale in **Appendix J.** Any abnormalities such as corneal infiltrates or opacities, and degree of re-epithelialization should be recorded.

**BSCVA** (Best Spectacle Corrected Visual Acuity) shall be measured using the Vector Vision 100% contrast ETDRS charts with the Vector Vision self-calibration, backlit light box at a test distance of 4 meters and calibrated to a photopic luminance of 85 cd/m² (80-110 cd/m²). The ambient room lighting shall be set from dim to dark illumination. BSCVA testing is to be performed with the ETDRS 4.0-meter manifest refraction in place; no refractive adjustment is necessary for BSCVA measurement. Detailed instructions for performing BSCVA testing are provided in **Appendix E**. A conversion chart for distance visual acuity testing between the number of correctly-read ETDRS and Snellen/Decimal acuity is provided in **Appendix D**.

**Contrast Sensitivity** shall be measured with the Vector Vision CSV 1000 at 8 feet under mesopic lighting conditions with and without glare and under photopic conditions without glare at spatial frequencies of 1.5, 3, 6, 12 and 18 cpd. See Reference **Appendix N** for full instructions.

**Corneal Topography** shall be measured with the iDesign System and a Scheimpflug (Pentacam) or Placido (Humphrey/ Zeiss Atlas) disk-based system. Images will be retained by the Investigator.

**Cycloplegic Refraction** shall be performed at least 30 minutes following installation of 1-2 drops of cyclopentolate 1% or tropicamide 1% to determine the subject's refraction without accommodation.

**Dilated Fundus Examination** shall be performed following installation of mydriatic agents approximately 30 minutes prior to determine the status of the ocular media, retina and lens.

iDesign Advanced WaveScan Studio System measures the refractive error and wavefront aberrations of the human eye using a Hartmann-Shack wavefront sensor. Preoperatively, a minimum of three measurements shall be taken to allow the iDesign system to select the exam for use in the generation of the treatment profile; a minimum wavefront diameter of 4.0 mm for preoperative measurements is required. Postoperatively, at least one measurement is required at designated study exams. Every

17NOV2015/ 3.0 42 PR/STAR-115-MIPS

effort shall be made to obtain measurements with the largest wavefront diameter possible at each visit.

**Schirmer I Tear Test (with anesthetic)** is to be performed before applanation tonometry, ultrasonic pachymetry and other procedure that may irritate the cornea. See **Appendix M** for instructions on how to perform the Shirmer I Tear Test.

**Intraocular pressure** is to be measured using applanation tonometry and is to be performed after manifest refraction, vision tests, keratometry, topography, aberrometry, and biomicroscopy.

**Keratometry** (not simulated K) shall be conducted using the iDesign System and an auto or manual keratometer. The same keratometry method is to be used at each required visit, e.g., if auto keratometry was recorded at the preoperative exam, all postoperative keratometry readings should be auto K's. Do not use "sim K" from a corneal topography unit other than the iDesign system.

**Lighting levels and lane calibration** will be assessed by a representative of the Sponsor to ensure the lane length and lighting conditions are consistent across sites. The site or Sponsor designee will verify ambient room lighting is dim to dark illuminance with photopic chart background luminance level of 85 cd/m^2 (80-110 cd/m^2) with a light meter at least annually during the active enrollment and follow-up period. Verification of the chart luminance level will be done.

**Manifest Refraction** is to be performed using the phoropter or trial frames and the 100% ETDRS charts and the self-calibrating, backlit box at a distance of 4.0 meters and calibrated to a photopic luminance of 85 cd/m² (80-110 cd/m²). The ambient room lighting shall be set from dim to dark illuminance. Manifest refraction is to be performed using the Maximum Plus refraction method as detailed in **Appendix E**. Because 4.0 meters is not optical infinity, refraction adjustments are necessary for some vision tests to ensure proper vision testing taking into account test distance and the ETDRS refraction distance (4 m). **Appendix G** lists the refraction adjustments required for the various different vision tests using the ETDRS 4.0-meter refraction.

**Ocular Surface Disease Index (OSDI)** is a 12-question patient reported outcomes (PRO) instrument designed to measure severity of dry eye symptoms.

Patient Reported Visual Symptom Questionnaire (PRVSQ) (2015 version for PRK/LASIK) is a self-administered, questionnaire designed to measure patient reported occurrence and level of bother related to ocular visual symptoms. Severity of patient reported ocular visual symptoms area also assessed under different situations including with and without correction and under mesopic conditions.

17NOV2015/ 3.0 43 PR/STAR-115-MIPS

National Eye Institute Refractive Error Quality of Life Instrument – 42 (NEI-RQL-42) (2001 version) is a self-administered assessment tool designed specifically for those who through correction of refractive error have normal visual acuity, but may still be experiencing problems in vision-related functioning and well-being. The NEI-RQL questionnaire is to be administered before any other visual assessment or exam both preoperatively and at designated postoperative study exams.

**Pachymetry** to measure the central corneal thickness shall be performed with an ultrasonic pachymeter preoperatively and postoperatively as described in **Appendix A**.

**Photopic Luminance** is defined as 85 cd/m^2 (acceptable range of 80-110 cd/m^2).

**Mesopic Pupil Size** shall be measured using the iDesign System.

**Refractive Stability (preoperative)** is defined as a change of ≤1.00 D in MRSE (based on a previous exam, medical records, lensometry or prescription) at least 12 months prior to the preoperative manifest refraction.

Refractive Stability Check for Contact Lens Wearers is based on a change of not more than 0.50 D in manifest refractive sphere and cylinder as well as keratometric meridian (either axis) between 2 separate measurements at least 7 days apart with readings following cessation of contact lens wear of 4 weeks for rigid contact lenses (toric or spherical) and 2 weeks for soft contact lenses (toric or spherical).

**iDesign Treatment Planning** is required prior to the operative exam. All eyes will be targeted for emmetropia and undergo a "Surface PRK" treatment. The iDesign System will be used to create a treatment shape for each eye that qualifies for the study. The iDesign software used in this study is Version 1.3, in international configuration, with no physician adjustments.

**UCVA (Uncorrected Visual Acuity)** shall be measured using the Vector Vision 100% contrast ETDRS charts with the Vector Vision self-calibration, backlit light box at a test distance of 4 meters and calibrated to a photopic luminance (80-100 cd/m²) The ambient room lighting shall be set from dim to dark illuminance. UCVA testing is to be performed through a +0.25 D trial lens refractive adjustment to compensate for optical infinity. Detailed instructions for performing UCVA testing are provided in **Appendix H**. A conversion chart for distance visual acuity testing between the number of correctly-read ETDRS and Snellen acuity is provided in **Appendix D**.

17NOV2015/ 3.0 44 PR/STAR-115-MIPS

# APPENDIX D CONVERSION CHARTS FOR VECTOR VISION CHARTS

# **Conversion Reference Chart for Vector Vision Distance Chart at 4.0 Meters**

Standard	Number of				
Snellen	Letters				
	Read At				
20/	4 Meters				
(Decimal)	(13 Feet)				
	(ETDRS)				
10	55				
10	54				
11	53				
12	52				
12	51				
13	50				
13	49				
14	48				
14	47				
15	46				
16	45				
17	44				
17	43				
18	42				
19	41				
20 (Decimal 1.0)	40				
21	39				
22 (Decimal 0.9)	38				
23	37				
24	36				
25 (Decimal 0.8)	35				
26 28	34				
29 (Decimal 0.7)	33 32				
30	31				
32	30				
33 (Decimal 0.6)	29				
35 (Bedinal 6.6)	28				
36	27				
38	26				
40 (Decimal 0.5)	25				
42	24				
44	23				
46	22				
48	21				
50 (Decimal 0.4)	20				
53	19				
55	18				
58	17				
60	16				
63	15				
66 (Decimal 0.3)	14				
69	13				
73	12				
76	11				
80	10				
83	9				

Standard Snellen 20/ (Decimal)	Number of Letters Read At 4 Meters (13 Feet) (ETDRS)			
87	8			
91	7			
96	6			
100 (Decimal 0.2)	5			
105	4			
110	3			
115	2			
121	1			
126	0			

# APPENDIX E MAXIMUM PLUS MANIFEST REFRACTION TECHNIQUE WITH CYLINDER REFINEMENT

Manifest refraction testing will be performed using a self-illuminating light box calibrated to a photopic luminance of 85 cd/m² (80-100 cd/m²) and 100% contrast ETDRS charts designed for 4.0 meters. The ambient room lighting shall be set to dim to dark illuminance. NOTE: Objective refraction by iDesign measurement must be used as a starting point for the Manifest Refraction. Always ensure that the endpoint of refraction is maximum plus (or minimum minus) power that yields maximum visual acuity.

- 1) Occlude the fellow eye.
- 2) Place the iDesign system (4 mm Rx Calc) sphere (adjusted to 4 meters) and cylinder power and axis from the iDesign exam (vertex distance at 12.5mm) selected for treatment in the phoropter or trial frame
- 3) SPHERE: Starting with the objective refraction, refine the sphere to yield best visual acuity.
- 4) CYLINDER AXIS: Refine cylinder with a cross-cylinder and the objective cylinder refraction as the starting point. Refine axis first and power second, since the correct axis can be found with an incorrect power, but the correct power cannot be found with an incorrect axis.
  - a. Direct the subject's attention to 1 line above (larger letters) the best visual acuity. With the trial cylinder (axis and power) in the phoropter, introduce cross-cylinder for axis refinement. When asking the subject which cross-cylinder axis position is better, "one or two?", remind the subject to look at different letters on the line and report preference based on the overall clarity of the letters.
  - b. Refine the axis based on the subject's responses, using small steps (less than five degrees), until the subject reports no difference in the two choices.
- 5) CYLINDER POWER: Set the cross cylinder to refine cylinder power and present choices to the subject, remind the subject to look at different letters on the line and report preference based on overall clarity of the letters. Reduce or increase trial cylinder power accordingly.
  - a. Maintain the spherical equivalent throughout cylinder power refinement by adjusting the sphere once for every two clicks of cylinder power change.
- 6) SPHERE CHECK: Introduce fogging lens (typically +0.75D sphere) and reduce in 0.25D steps until visual acuity shows no improvement.

17NOV2015/ 3.0 46 PR/STAR-115-MIPS

## APPENDIX F CYCLOPLEGIC REFRACTION TECHNIQUE

The baseline refraction and the amount of accommodation that the subject habitually employs can only be determined by refracting with and without cycloplegia. The chief benefit of cycloplegia, therefore, is that it reduces accommodation so that the examiner can make an accurate measurement of the refraction in the un-accommodative state. By comparing this result with a manifest refraction, the true refractive state of the eye and the accommodative tone can be established.

There are two pieces of information that are available from the cycloplegic examination that cannot be deduced from the manifest refraction alone:

- the magnitude of the refractive error free from the influence of accommodation and,
- the extent to which the accommodative tone influences the refractive state.

The following cycloplegic refraction technique is to be used throughout the study:

- 1. Instill 1-2 drops of cycloplegic agent (cyclopentolate 1% or tropicamide 1%) and wait at least 30 minutes to allow for a full cycloplegic effect.
- 2. Start with the Manifest Refraction (maximum plus; refined from the objective iDesign measurement).
- 3. Refine the sphere magnitude so the least minus yields the most letters. It is required that you do not refine the cylinder axis or the cylinder power.

17NOV2015/ 3.0 47 PR/STAR-115-MIPS

## APPENDIX G REFRACTION ADJUSTMENTS

Postoperative study manifest refractions are to be performed using the 100% ETDRS charts at a distance of 4.0 meters. Because 4.0 meters is not optical infinity, refraction adjustments are necessary to ensure proper vision testing taking into account test distance and refraction distance. The adjustment required (in diopters) is 1/test distance (in meters). To adjust a 4.0-meter manifest refraction to optical infinity, -0.25 D is to be added to the sphere of the refraction to obtain a true distance (infinity) correction. When testing uncorrected visual acuity at 4.0-meters a +0.25 D sphere is required. In the case where the manifest refraction distance (4.0 meters) and the vision test distance (4.0 meters) are the same, no adjustment is necessary. The following table lists the refraction adjustments required for the various vision tests in this study:

# **Refraction Adjustments for Vision Testing**

Vision Test	Test Distance	Correction/Adjustment
Uncorrected distance visual acuity (UCDVA)	4.0 m	+0.25 D adjustment only
Best corrected distance visual acuity (BCDVA)	4.0 m	No adjustment; ETDRS Rx only
Best corrected contrast sensitivity	8.0 ft (2.5 m)	+0.12 D added to ETDRS sphere Rx

17NOV2015/ 3.0 48 PR/STAR-115-MIPS

# APPENDIX H INSTRUCTIONS FOR USE OF VECTOR VISION ETDRS DISTANCE VISUAL ACUITY CHART

Distance visual acuity testing will be performed using the Vector Vision CSV-1000 retroilluminated light box and 100% contrast ETDRS (Early Treatment Diabetic Retinopathy Study) distance charts at a test distance of 4.0 meters (13 feet). All subjects will be tested both uncorrected monocularly and binocularly, it is recommended that monocular testing be completed before binocular testing.

The CSV-1000 light box is self-illuminated and self-calibrates to a light level of 85 cd/m^2 (a range of 80-110 cd/m^2 is acceptable). Room lighting is to be set lower than the illumination from the light box, per the manufacturer's instructions. Ambient illuminance should be from dim to dark to maximize pupil size. No surface (including reflective surfaces) within the subject's field of vision should exceed the chart background in luminance.

The light box must be placed 4.0 meters from the subject for testing distance visual acuities. Reverse charts are available for rooms that require "folding" via a mirror to reach a distance of 4.0 meters. Whether standard or "folded," if the room set-up does not allow the chart to be placed precisely at 4.0 meters, record the actual test distance used (e.g., 3.9 meters), and visual acuity measurements will be mathematically adjusted by AMO for the actual test distance used.

Refraction adjustments should be used as necessary for the 4.0 meters visual acuity test distance. As manifest refractions are to be performed using the ETDRS chart at 4.0 meters, no adjustment is required to the refraction when testing BCDVA at 4 meters. However, as 4 meters is not optical infinity, an adjustment of +0.25 D sphere is required to test UCDVA at 4 meters (1/test distance in meters = adjustment in diopters).

To test subjects monocularly, occlude the fellow eye in the phoropter or with an occluder (if trial lenses are used). To measure visual acuity, subjects should be instructed to start with the smallest line where they can read all of the letters. If they miss any letters, go up a line until they are able to read all the letters on a line, then continue to read each subsequently smaller line. The subject should be encouraged to read as many letters possible, even if they have to guess. Testing may be stopped when it is evident that no further readings can be made. Record the total number of letters read correctly on the chart. Score sheets similar to the example below will be provided for the study. To score the visual acuity, draw a line through each letter missed (or circle letters read correctly) and then tally the total number of letters correctly read. Scoring sheets must be used and retained as source documentation. A conversion chart is provided on the scoring sheet for reference between the number of correctly-read ETDRS letters and Snellen equivalents. (Appendix D).

17NOV2015/ 3.0 49 PR/STAR-115-MIPS

TO AVOID MEMORIZATION: charts will be changed between visual acuity tests.

# **Example of ETDRS Score Chart**

ETDRS Chart #1 Line						RUNNING TOTAL	NUMBER READ
1	Ν	С	K	Z	0	5	
2	R	Η	S	D	K	10	
3	D	0	V	Н	R	15	
4	С	Z	R	Н	S	20	
5	Ο	Ν	Н	R	С	25	
6	D	K	S	Ν	V	30	
7	Z	S	0	K	Ν	35	
8	С	K	D	Ν	R	40	
9	S	R	Z	K	D	45	41
10	Ħ	Z	0	¥	C	50	
11	Н	¥	Đ	0	K	55	

## APPENDIX I INSTRUCTIONS FOR KERATOMETRY

Every effort should be made to obtain keratometry readings from the iDesign system at every visit in addition to auto and/or manual keratometry. Keratometry must be performed prior to dilation and any contact with the cornea (e.g., tonometry or pachymetry) as follows:

- 1. Measure keratometry using the iDesign System and also perform an auto or manual keratometry reading. If possible use the same method at each required visit, e.g., if auto keratometry was recorded at the preoperative exam, all keratometry readings postoperatively should be auto K's in addition to those from the iDesign system.
- 2. Do not use "sim K"s from a corneal topography unit.
- 3. Always record the flat meridian (smaller number, e.g., 42.25) as K1. Record the steeper meridian (larger number, e.g., 43.00) as K2 along with the corresponding axis (e.g., 42.25 / 43.00 x 165).
- 4. Record spherical corneas by placing the corneal curvature values in both K1 and K2 and marking axes 180 attached to K2 (e.g., 44.00 / 44.00 x 180). Spherical Ks will not be accepted with axes other than 180 (do not use 0).

17NOV2015/ 3.0 51 PR/STAR-115-MIPS

# APPENDIX J SLIT-LAMP EXAM GRADING SCALE

# A. Corneal Clarity

Below is the grading scale to be used for corneal clarity:

Grade	Description
0.0	Clear
0.5	Faint/trace haze
1.0	Mild haze, not affecting refraction
2.0	Moderate haze, refraction possible
3.0	Dense haze/ prevents refraction, AC visible
4.0	Dense haze/AC not visible

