## Safety

## 1. MAINTENANCE OF BSCVA-LINES LOST

- Success criteria: <5% of eyes with a loss of >2 lines of BSCVA from preoperative
- Success criteria: <1% of eyes with haze beyond 6 months with loss >2 lines of BSCVA

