#### PERIODIC POSTOPERATIVE EXAMINATION PROCEDURES

Periodic examinations will be conducted at 1, 3, 6, 9, and 12 months after treatment. In the event that extended follow-up is not needed, the follow-up period may be reduced.

Note: Subjects are not to wear contact lenses postoperatively until after completion of the study. Wearing contact lenses may potentially cause wavefront or topography changes that may influence the visual acuity results. During the study, if correction is required, spectacles should be prescribed.

The following data shall be assessed and recorded during the periodic examinations, although not all are required at all periodic visits (see also **Appendix A**). General descriptions and requirements of the various tests are provided in **Appendix C**. Non-directed responses to the open-ended question "Are you having any difficulties with your eyes or vision?", followed by all patient reported outcome questionnaires, followed by the iDesign measurement, are to be administered first before any other ocular examinations. All non-contact procedures (e.g. topography and keratometry) will be performed before contact assessments (e.g. IOP and pachymetry). If required, cycloplegic refraction/fundus exam will be the final procedures performed at the study visits.

- Ocular and systemic medical history and concomitant medications
- Non- directed ocular/visual symptoms (from non-directed responses obtained from the open-ended guestion "Are you having any difficulties with your eyes or vision?").
- Binocular Subjective Questionnaires: OSDI, PRVSQ for PRK/LASIK, NEI-RQL-42 and exploratory Satisfaction Questionnaire (Note: For reliability validation purposes the PRVSQ will be completed by the subject at the visit and also at home 7 days after the 3-month visit and mailed back to the site.)
- iDesign System Measurement (refraction, aberrometry, topography, keratometry, pupillometry)
- Keratometry (iDesign and auto/manual)
- Corneal Topography (Humphrey/Zeiss Atlas or Pentacam)
- UCVA photopic, monocular, distance (ETDRS)
- UCVA photopic, binocular, distance (ETDRS)
- Manifest Refraction (ETDRS)
- BSCVA photopic, monocular, distance (ETDRS)
  - At 3 months or later, if there is a loss of 2 or more lines of BSCVA (≥ 10 letters)
    compared to the preoperative visit, a rigid contact lens over refraction should be
    performed to determine if the BSCVA loss is due to irregular astigmatism. If a

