    rigid contact lens over refraction is not medically advisable, then a pin-hole acuity
    should be obtained
- Monocular distance corrected contrast sensitivity substudy

17NOV2015/ 3.0 21 PR/STAR-115-MIPS

- Mesopic with and without glare at 1.5, 3, 6, and 12 cpd
- Photopic without glare at 3, 6, 12, and 18 cpd
- Anterior Segment Examination
- Schirmer I Tear Test (with anesthetic)
- Intraocular pressure (applanation tonometry)
- Pachymetry (ultrasound) (1 and 12-months only)
- Cycloplegic Refraction (6 and 12-months only)
- Dilated Fundus Examination (6 and 12-months only)
- Adverse Events and Complications
- Device Deficiencies/Complaints

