2 ANALYSIS POPULATIONS

2.1 ANALYSIS POPULATIONS/HANDLING OF MISSING DATA

The safety population will be the primary analysis population for all endpoints and includes all eyes that receive study treatment. However, if there are greater than 5% of eyes with missing study exams at the stability time point, an intent-to-treat (ITT) population will be used as the primary analysis population for the primary effectiveness endpoints. In this case, missing data will be imputed. For continuous variables, the planned method to use is the MCMC full-data imputation as described in Little & Rubin¹. For data with a binary response and a monotone missing pattern, the planned method is to use the monotone logistic regression multiple imputation method. Data imputation and analysis will be performed using the MI and MIANALYZE procedures² in SAS[®] (Version 9.2).

¹ Little, R. and Rubin, D. Statistical Analysis with Missing Data, John Wiley & Sons, Inc. New York, Second Edition, (2002)

² SAS Institute. The MI and MIANALYZE Procedures. SAS/STAT 9.2 User Guide. and SAS/STAT User Guide for the MI Procedure: Imputation Methods. Cary, N.C.

In addition to the above imputation methods, sensitivity analyses using different imputation approaches will also be performed for primary effectiveness endpoints for the ITT population. A worst-case scenario with the worst score assigned to the missing data will be performed. A tipping point analysis will also be performed.

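### An eye whose corneal haze prevents refraction has no protocol BSCVA, and no rule counts it as an event in the three BSCVA-based safety criteria

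*Protocol*

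**What the plan says.** - **Grading.** In Protocol Appendix J, grade 2.0 is the last grade at which refraction is described as possible. Grade 3.0 is "Dense haze/ prevents refraction, AC visible". Grade 4.0 is "Dense haze/AC not visible" and does not mention refraction.
- **Measurement.** Protocol Appendix C states that "BSCVA testing is to be performed with the ETDRS 4.0-meter manifest refraction in place". MRSE comes from the same refraction.
- **Criteria.** Protocol 6.1 sets "<5% of eyes with a loss of >2 lines of BSCVA from preoperative", "<1% of eyes with haze beyond 6 months with loss >2 lines of BSCVA", and a further limit of under 1% for eyes that start at 20/20 or better and end worse than 20/40. Protocol 20.2 and SAP 5.2 repeat the three limits. Both word the last acuity cut slightly differently, which does not affect this point.
- **Fallback acuity.** Protocol 10.6 asks for a rigid-lens over-refraction, or a pinhole acuity where that is not advisable. The condition opens "At 3 months or later, if there is a loss of 2 or more lines of BSCVA (≥ 10 letters", so a measured BSCVA comes first. Neither result is said to replace BSCVA.
- **Missing data.** SAP 2.1 makes all treated eyes the primary population. If more than 5% of eyes have missing exams at the stability time point, an ITT population is used for the primary effectiveness endpoints, and "In this case, missing data will be imputed". The worst-case and tipping-point analyses also cover only those endpoints. The safety endpoints have no missing-data rule.

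**The concern.** The haze criterion is a safety limit, and corneal haze is named in the clinical hypothesis (Protocol section 3). Under the stated rules, an eye with moderate haze can be refracted, can show a loss of more than 2 lines and can count. An eye with denser haze cannot be refracted, so no loss can be computed and nothing makes it count. The outcome itself causes the gap in measurement, and in these criteria the gap can only favour the device. Without a rule, scoring would be settled after the data are seen, on limits that a few eyes decide.

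**Working it through.** **Inputs.** 300 evaluable and 334 treated eyes (Protocol 20.6); limits of <1%, <1% and <5% (Protocol 6.1); 5% trigger for the ITT analysis (SAP 2.1).

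**The plan's own figure.** 300 / (1 − 0.10) = 333.3, rounded up to 334. This matches Protocol 20.6.

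**Events that the limits allow.** All three limits are strict inequalities.

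| Limit | n = 300 | n = 334 |
|---|---|---|
| <1% | 2 pass (0.67%); 3 fail (1.00%) | 3 pass (0.90%); 4 fail (1.20%) |
| <5% | 14 pass (4.67%); 15 fail (5.00%) | 16 pass (4.79%); 17 fail (5.09%) |

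**Effect of k eyes that cannot be refracted.** Let x be the number of measured events. Excluded, the rate is x/(n − k). Kept as non-events, it is x/n. Counted as events, it is (x + k)/n. The documents do not give k; the range of 1 to 4 is an assumption.

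| n | x | k | Excluded | Kept as non-event | Counted as event |
|---|---|---|---|---|---|
| 300 | 2 | 1 | 2/299 = 0.67% | 2/300 = 0.67% | 3/300 = 1.00%, fails |
| 300 | 1 | 2 | 1/298 = 0.34% | 1/300 = 0.33% | 3/300 = 1.00%, fails |
| 300 | 0 | 3 | 0% | 0% | 3/300 = 1.00%, fails |
| 334 | 3 | 1 | 3/333 = 0.90% | 3/334 = 0.90% | 4/334 = 1.20%, fails |
| 334 | 2 | 2 | 2/332 = 0.60% | 2/334 = 0.60% | 4/334 = 1.20%, fails |
| 334 | 0 | 4 | 0% | 0% | 4/334 = 1.20%, fails |

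The excluded and kept-as-non-event columns pass the <1% limit in every row, so the point does not depend on which denominator is used. Treatment is bilateral and intended for the same day (Protocol 10.5), so one subject affected in both eyes would supply k = 2.

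**The <5% limit.** Only the boundary moves: 14/299 = 4.68% passes and 15/300 = 5.00% fails.

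**MRSE, for comparison.** 5% of 334 is 16.7, so up to 16 eyes can be missing before the ITT rule applies. With three such eyes, a borderline 249/331 = 75.2% becomes 249/334 = 74.6%, a shift of under 1 point.

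**The case against.** Five arguments on the other side deserve weight.

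1. **Another criterion may catch these eyes.** Serious, device-related adverse events must also stay below 1% of eyes, cumulatively, and that count needs no BSCVA. Sight-threatening events and permanent impairment are serious (Protocol 11.1), and a possible relation to the device is enough (11.4). This stands in part. Whether such an eye is counted rests on the investigator's judgment of seriousness and cause. The anticipated adverse event for haze itself requires a BSCVA loss, so it does not close the gap. UCVA and the clarity tables would show the eye, but neither carries a safety limit.

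2. **An acuity might still be recorded.** The refraction starts from an iDesign prescription (Appendix E), and Appendix D extends to 0 letters. Against 40 letters at 20/20, a score of 0 is a change of (40 − 0)/50 = 0.80 logMAR, far beyond the 0.24 cut for more than 2 lines in SAP Appendix II. A site could do this, but nothing instructs it for an eye that cannot be refracted.

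3. **The number of eyes is likely to be very small.** The earlier wavefront-guided PRK study in Protocol section 2 reports no loss of 2 or more lines in 597 eyes. The one-sided 95% upper bound is 1 − 0.05^(1/597) = 0.50%. At that bound, 334 eyes give about 334 × 0.0050 = 1.7 expected events and roughly a 9% chance of four or more, if eyes are independent. This is only indicative: the aberrometer differed, the endpoint is acuity loss and not grade 3.0 haze, and that study may have had the same gap. It does make four such eyes an unlikely scenario.

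4. **All treated eyes are in the population.** A reader might infer that these eyes leave the denominator. No passage excludes them, and SAP 2.1 keeps all treated eyes. The population statement does not say how an unmeasured eye is scored, so the point survives without that inference.

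5. **The effectiveness endpoints are better protected.** A reader might also infer that MRSE would be imputed from earlier, clearer visits, or that the stability rate is biased. The documents do not state the predictors of the imputation model. Worst-case and tipping-point analyses exist once the ITT population is used, and the effect on MRSE is trivial for a few eyes. Stability is defined on eyes with data at the relevant visits, so an eye without paired refractions falls outside those cohorts by design.

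**Conclusion.** The point holds for the three BSCVA-based safety criteria and should be confined to them. Read as written, a grade 3.0 eye has no protocol BSCVA at an attended visit, and no rule counts it as an event. The two 1% limits are the exposed ones, because a single unscored eye can reverse a borderline result (2/299 = 0.67% against 3/300 = 1.00%; 3/333 = 0.90% against 4/334 = 1.20%). With no measured events it would take three eyes in 300 or four in 334, and the documents give no support for expecting that many.

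The conclusion rests on taking the grade 3.0 descriptor literally and on no acuity being recorded by another route. Extending it to grade 4.0 is an inference from that grade being worse. The size is conditional: nothing changes if no such eye occurs. The documents do not support a broader claim about lost denominators, MRSE or stability.

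**What to change.** Add to SAP 5.2: an eye graded 3.0 or worse for corneal clarity at the analysis visit, for which refraction was not possible and no BSCVA was obtained, stays in the denominator. It counts as an event for loss of more than 2 lines and for BSCVA worse than 20/40. Where the haze is present beyond 6 months, it also counts as an event for the haze criterion. An eye with a recorded BSCVA is scored on that value.

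The stability definition should stay as it is. Scoring such eyes as MRSE non-successes is optional and would hardly move the result.

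The cost is one scoring rule, based on slit-lamp grades that are already collected and a record that refraction was not possible. It adds no visit or test and does not change care. The downside is that an eye whose acuity could not be measured is assumed to have failed.
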